3.2.1.4. Safety Review Meetings

Investigators will communicate with the Sponsor any incidence of DLT on a real-time basis.

Safety review meetings (SRMs) will include at least the Investigators and the Sponsor's medical monitor.

During Dose Escalation, SRMs will occur as needed to make determinations about enrollment and dose escalation according to the DLT-dependent mCRM, and to determine the RDE.

During Dose Expansion, SRMs will occur as needed to assess safety and tolerability of the selected RDE.

3.2.1.5. Stopping Rule for Recommended Dose for Expansion Determination

Dose Escalation will be stopped if any of the following occur:

- a. at least 6 evaluable subjects have been enrolled at the RDE level with at least 18 evaluable subjects, in total, enrolled in Dose Escalation, OR
- b. at least 9 evaluable subjects have been enrolled at a particular dose level, the model recommends continuing at the same dose level, and the posterior probability of the DLT rate falling within the target DLT interval is $\geq 50\%$.
The target DLT interval is defined as $16\% < \text{DLT rate} \leq 33\%$
(Section 11.11.3), OR
- c. the initial dose level is too toxic.

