^b Administer with a meal, with 240 mL of water. On the morning of Endpoint ECG days, breakfast should be started 30 minutes prior to dosing and should be completed within approximately 20 minutes. For all other dosings, it is recommended that meals (breakfast or dinner) be completed within approximately 30 minutes, and DS-1205c should be taken immediately after meal completion. Doses of DS-1205c should be taken approximately 12 hours apart.

^c Co-administer with morning dose of DS-1205c.

Dose escalation will be guided by the modified Continuous Reassessment Method (mCRM) using a Bayesian logistic regression model (BLRM) following the escalation with overdose control (EWOC) principle. In this method, a decision to escalate to the next cohort is based on review of all subjects who have completed the dose-limiting toxicity (DLT)-evaluation period.

The DLT-evaluation period is defined as the 7 days of Cycle 0 plus the 21 days of Cycle 1 (28 days total). A DLT-evaluable subject is defined as a subject who has received DS-1205c and EITHER has completed minimum safety evaluation requirements over the DLT-evaluation period OR has experienced a DLT during the DLT-evaluation period.

The RDE will be decided based on an overall assessment of available safety and tolerability data from Cycle 1 and beyond, and all available PK, biomarker, and tumor response data. Dose Escalation will be stopped if any of the following occur: (a) at least 6 evaluable subjects have been enrolled at the RDE with at least 18 evaluable subjects in total enrolled in Dose Escalation, or (b) at least 9 evaluable subjects have been enrolled at a particular dose level, the model recommends continuing at the same dose level, and the posterior probability of the DLT rate falling within the target DLT interval is $\geq 50\%$, or (c) the starting dose is too toxic.

Study Duration:

Dose Escalation

- Enrollment is planned to occur over approximately 12 months.
- Treatment and follow-up will be completed when all subjects have either discontinued study treatment or completed last study visit

The number of treatment cycles is not fixed in this study. Subjects will continue study treatment until withdrawal of consent, progressive disease (PD), or unacceptable toxicity for all subjects in Dose Escalation and Dose Expansion.

Study Sites and Locations: Approximately 20 clinical sites within Japan. Additional sites and countries may be added as needed.

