3.2.1.6. Determination of Recommended Dose for Expansion

Once the dose escalation stopping criteria are met, the RDE determination will be guided by mCRM using a BLRM with EWOC (Section 3.2.1.2). The RDE will be decided based on an overall assessment of available safety data from Cycle 1 and beyond, and all available PK, biomarker, and tumor response data.

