11.9. Sample Size Determination

Phase 1 dose escalation : ≥ 18 subjects

The Dose Escalation part of this study consists of mCRM with EWOC design with at least 3 DLT-evaluable subjects per dose level. At least 18 DLT-evaluable subjects are needed to reach an accurate estimate of the maximum tolerated dose (MTD). There will be at least 18 DLT-evaluable subjects treated to reach an accurate estimate of the RDE in Dose Escalation, with at least 6 subjects treated at the final selected dose.

CCI

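### The dose-escalation stopping rules do not guarantee the 18 DLT-evaluable subjects, or the 6 at the final dose, that section 11.9 states

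*Combined protocol and SAP*

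**What the plan says.** Section 3.2.1.5 lists three alternative reasons to stop escalation.

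- Rule (a): "at least 6 evaluable subjects have been enrolled at the RDE level" "with at least 18 evaluable subjects, in total, enrolled in Dose Escalation". The synopsis (Study Design) has the same condition: "at least 6 evaluable subjects have been enrolled at the RDE with at least 18 evaluable subjects in total enrolled in Dose Escalation".
- Rule (b): "at least 9 evaluable subjects have been enrolled at a particular dose level", the model recommends staying at that level, and the posterior probability that the DLT rate lies in the target interval (16% to 33%) is at least 50%.
- Rule (c): the starting level is too toxic.

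Section 3.2.1.6 then gives the order of events: "Once the dose escalation stopping criteria are met, the RDE determination will be guided by mCRM using a BLRM with EWOC". The decision itself is an overall assessment that uses safety from Cycle 1 onward and "all available PK, biomarker, and tumor response data".

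Section 11.9 requires at least 3 DLT-evaluable subjects per dose level. It says that at least 18 DLT-evaluable subjects will be treated, "with at least 6 subjects treated at the final selected dose".

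Section 3.2.1.2 permits, but does not require, any cohort to be expanded. It also allows backfilling during Dose Escalation to lower doses already shown to be safe, and the use of lower or intermediate levels.

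**The concern.** Section 11.9 presents 18 and 6 as facts about the completed escalation, but no operating rule enforces them.

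- Rule (a) counts subjects at a dose that, under 3.2.1.6, is named only later.
- If that dose is read as the model's current recommendation, the rule can be applied. The final choice may still be another level, and nothing requires that level to be filled to 6.
- Rule (b) has no condition on the level finally chosen and no minimum total.

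The RDE is part of the primary objective, and section 3.2 gives it to every Dose Expansion subject. A reader of 11.9 would believe that at least 6 evaluable subjects stand behind it. The rules allow 3, or none if an untested intermediate level is selected.

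**Working it through.** **Inputs.** From 3.2.1.5: 6 at the RDE level with 18 in total (rule a), or 9 at one level with target probability of at least 0.50 (rule b). From 11.9: a minimum of 3 per level. From 11.11.1 and 11.11.2: logit π(d) = log α + β·log(d/800). The prior on (log α, log β) is bivariate normal with means (-1.1493, -0.5514), SDs (2.0739, 1.5228) and correlation -0.1943. From 11.11.3: recommend the dose with the highest probability of a DLT rate in 0.16 to 0.33, among doses with P(DLT rate > 0.33) below 0.25. Dose d is taken as mg per BID administration. Posteriors were computed by grid integration.

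**1. The plan's own figures.** The documents give no formula or operating characteristics for 18 and 6, so these cannot be reproduced; they are stated minimums. The model does reproduce. At 800 mg the slope term is zero, so the prior median is 1/(1 + e^1.1493) = 24.1%. At 200 mg it is 8.0%. The plan states approximately 24.5% and 8%.

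**2. Counting.** With 3 per level, 3 + 3 + 3 + 9 = 18. Eighteen subjects can leave three of the four provisional levels with 3 each.

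**3. Rule (b).** Take DLTs of 0/3, 0/3 and 3/9 at 200, 400 and 600 mg BID, one DLT in each cohort of 3 at 600.

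| Level | P(target) | P(DLT rate > 0.33) |
|---|---|---|
| 600 mg BID | 0.53 | 0.20 |
| 800 mg BID | 0.42 | 0.43 (excluded) |

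The model stays at 600, which has 9 subjects, and 0.53 is at least 0.50, so rule (b) is met. The total is 3 + 3 + 9 = 15, below 18. Each other tested level holds 3.

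**4. Rule (a), reading the RDE level as the model's current dose.** Take 0/3, 0/3, 1/6 and 2/6 at 200, 400, 600 and 800 mg BID, total 18. At 800, P(target) is about 0.50 and P(DLT rate > 0.33) is 0.23. At 600, P(target) is 0.41. The model recommends 800, which has 6, so rule (a) is met. Section 3.2.1.6 does not tie the RDE to that level, and two of the other three levels hold 3.

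**5. DLT data alone.** Take n = 3/3/9/3 with DLTs 0/0/2/0, total 18. At 800, P(target) is 0.38, the highest, and P(DLT rate > 0.33) is 0.08. The model recommends 800, which has 3. If rule (a) counts the model's current dose, it is not met and enrollment continues. If it counts some other working candidate, such as 600 with 9, it is met, and the model then points to a level with 3. The wording does not say which applies.

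**6. Frequency.** This used 4,000 simulated trials per scenario. Assumptions not in the documents: cohorts of 3, no skipped level, only the four provisional doses, no backfilling, and the true DLT rates shown.

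| True DLT rates (%) | Model dose has < 6 at 18 subjects | Rule (b) stop below 18 |
|---|---|---|
| 8 / 14 / 19 / 24.5 | 8.3% | 3.2% |
| 2 / 4 / 6 / 10 | 3.2% | 0.3% |
| 5 / 15 / 30 / 45 | 9.7% | 6.8% |
| 10 / 25 / 40 / 55 | 6.2% | 5.9% |

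If the overall assessment then chose one level below the stopping dose, that level held fewer than 6 in about 59% to 84% of trials stopped under (a) or (b). This range depends entirely on the assumed step down.

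**7. Model evidence at an under-filled level.** At 400 mg BID, P(DLT rate > 0.33) is 0.015 in step 4 and 0.055 in step 3, with posterior mean DLT rates of 11% and 15%. Both probabilities are far below the 0.25 limit.

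**The case against.** **The RDE may be settled during escalation.** Section 3.2.1.4 has safety review meetings determine the RDE during Dose Escalation, so a working RDE can exist before the formal stop. This stands. A reader might infer that rule (a) is circular and cannot be applied, and the documents do not support that. It is an ambiguity about order and about which dose is counted. Section 3.2.1.4 sets no minimum number, however, and does not bear on rule (b).

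**Section 11.9 may bind on its own.** It is worded as a commitment, and 3.2.1.2 lets cohorts be expanded as required, so a sponsor selecting an under-filled level could be expected to fill it. That is a fair reading of intent. But expansion is optional, and rules that can end escalation without meeting a commitment still need reconciling with it.

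**A different final dose is an inference.** Section 3.2.1.6 says the choice is guided by the model and does not describe moving to another level. It does admit other data, though, and does not confine the RDE to the level that triggered stopping.

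**The safety evidence is stronger than 3 subjects suggest.** A reader might compare exact one-sided 95% upper limits: 1 - 0.05^(1/3) = 63% after 0/3, against 1 - 0.05^(1/6) = 39% after 0/6. The reader might then infer an uncontrolled DLT risk at the RDE. The documents do not support this, because the design pools all levels through a monotone dose-toxicity model. In step 4, 12 further subjects were treated at higher doses; in step 3, 9 were. This objection stands in full, and stand-alone binomial limits should not be used to size the problem.

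**Conclusion.** The point holds as a mismatch between 3.2.1.5, 3.2.1.6 and 11.9. The rules deliver neither 18 in total nor 6 at the final dose in every case. Rule (b) can stop at 15, and the chosen level can hold 3 evaluable subjects against the stated 6.

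The logical gap needs no assumptions. The examples rest on the plan's own model and prior, with d per BID administration. The simulated frequencies also rest on assumed DLT curves and conduct rules, and only indicate that the cases are not exotic.

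The consequence is limited. It is mainly less direct experience (safety, PK and response) at the dose taken into expansion than 11.9 tells the reader to expect. No view is taken on which dose should be chosen. The passages should be reconciled before the RDE is declared.

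**What to change.** Reconcile 3.2.1.5, 3.2.1.6, 11.9 and the synopsis. In rule (a) and its synopsis counterpart, replace the reference to the RDE level with *the dose level currently recommended by the model (11.11.3)*. Then take one of two routes.

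- **Restate 11.9** as: *at least 6 evaluable subjects at the model-recommended dose when escalation stops under rule (a), with at least 18 in total unless rule (b) or (c) stops escalation earlier.* This costs wording only.
- **Enforce the 6.** State in 3.2.1.6 that a level with fewer than 6 DLT-evaluable subjects is expanded to 6, under the cohort-expansion provision of 3.2.1.2, before it is declared the RDE. State also whether the total of 18 applies after a rule (b) stop. The cost is up to 6 - 3 = 3 more subjects at a tested level and up to 6 at an untested one. If 18 is kept after rule (b), a stop at 15 needs 18 - 15 = 3 in total, and subjects added to fill the chosen level count toward these.

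The second route should cite cohort expansion and not backfill. Backfill in 3.2.1.2 is limited to Dose Escalation and to lower doses already shown to be safe, so it may not apply once escalation has stopped.

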3.2.1.6. Determination of Recommended Dose for Expansion

Once the dose escalation stopping criteria are met, the RDE determination will be guided by mCRM using a BLRM with EWOC (Section 3.2.1.2). The RDE will be decided based on an overall assessment of available safety data from Cycle 1 and beyond, and all available PK, biomarker, and tumor response data.

3.2.2. CCI

[REDACTED]

[REDACTED]

[REDACTED]

3.2.2.1. Stopping Rule for Other Consideration(s)

The Sponsor has the right to terminate the study at any time, and study termination may also be requested by (a) competent authority(-ies).

3.3. Duration of Subject Participation

The Eligibility Screening period is up to 22 days for Dose Escalation Part and 30 days for Dose Expansion Part. Each cycle of treatment (except for Cycle 0 in Dose Escalation) is 21 days.

The number of treatment cycles is not fixed in this study. Subjects may continue study treatment until PD, unacceptable toxicity, withdrawal of consent, or other reasons detailed in Section [5.6.1](#).

[figure not shown]
3.4. Duration of Study

This study is expected to last approximately 3 years from the time the first subject is enrolled to the time the last subject is off the study. The end of the study is defined as the last subject visit or contact, including telephone contacts, for collection of any study-related data.

Dose Escalation

- Enrollment is planned to occur over approximately 12 months.
- Treatment and follow-up will be completed when all subjects have either discontinued study treatment or completed last study visit.

CCI

A large black rectangular redaction box covers the majority of the page below the 'CCI' text, starting just below the 'Treatment and follow-up' list and extending down to the bottom of the page.

4. STUDY POPULATION

Subjects must satisfy all of the following inclusion and exclusion criteria to participate in either Dose Escalation or Dose Expansion:

4.1. Inclusion Criteria

1. Male or female subjects aged 20 years and older.
2. Has histologically or cytologically documented adenocarcinoma NSCLC.
3. Has locally advanced or metastatic NSCLC, not amenable to curative surgery or radiation.
4. Has acquired resistance to EGFR TKI according to the Jackman criteria.³⁶
 - a. Historical confirmation that the tumor harbors an EGFR mutation known to be associated with EGFR TKI sensitivity (including G719X, exon 19 deletion, L858R, L861Q), OR
 - b. Has experienced clinical benefit from an EGFR TKI, followed by systemic progression of disease (RECIST version 1.1 or World Health Organization [WHO]) while on continuous treatment with an EGFR TKI.
5. Is currently receiving and able to interrupt gefitinib or discontinue erlotinib, afatinib, dacomitinib, or osimertinib.
6. Has been receiving gefitinib, erlotinib, afatinib, dacomitinib, or osimertinib for at least 6 weeks with well-controlled related toxicities less than Grade 3 in severity at the time of screening period. Subjects who have been receiving gefitinib must be taking gefitinib at a dose of 250 mg/day.
7. Has radiological documentation of disease progression while receiving continuous treatment with gefitinib, erlotinib, afatinib, dacomitinib, or osimertinib.
8. Has at least one measurable lesion per RECIST version 1.1.
9. Is willing to provide archival tumor tissue from a biopsy performed after progression during treatment with gefitinib, erlotinib, afatinib, dacomitinib, or osimertinib OR has at least one lesion, not previously irradiated, amenable to core biopsy and is willing to undergo screening tumor biopsy.
10. Demonstrates absence of EGFR T790M mutation in tumor tissue since progression during gefitinib, erlotinib, afatinib, dacomitinib, or osimertinib treatment.
11. Has ECOG PS of 0 or 1, with no deterioration over the previous 2 weeks. A table of the ECOG PS scale can be found in Appendix Section [17.4](#).
12. Has adequate bone marrow reserve and organ function, defined as:
 - a. Platelet count $\geq 100 \times 10^9/L$
 - b. Hemoglobin (Hb) $\geq 9.0 \text{ g/dL}$
 - c. Absolute neutrophil count (ANC) $\geq 1.5 \times 10^9/L$

- d. Prothrombin time and activated partial thromboplastin time (aPTT) $\leq 1.5 \times$ the upper limit normal (ULN), except for patients on coumarin-derivative anticoagulants or other similar anticoagulant therapy, who must have prothrombin time-International Normalized Ratio (PT-INR) within therapeutic range as deemed appropriate by the Investigator.
- e. Serum creatinine $\leq 1.5 \times$ ULN, or creatinine clearance ≥ 50 mL/min as calculated using the Cockcroft-Gault equation (Section 17.1); confirmation of creatinine clearance is only required when creatinine is $> 1.5 \times$ ULN.
- f. AST/ALT $\leq 3.0 \times$ ULN (if liver metastases are present, $\leq 5.0 \times$ ULN).
- g. Total bilirubin $\leq 1.5 \times$ ULN if no liver metastases or $< 3.0 \times$ ULN in the presence of documented Gilbert's Syndrome (unconjugated hyperbilirubinemia) or liver metastases.
- h. CK $< 1.5 \times$ ULN.
- i. Lipase $< 2 \times$ ULN.

13. Has adequate treatment washout period before first dose of study drug, defined as:

- a. QTc prolonging medications ≥ 10 days (Section 17.6)
- b. CYP3A4 strong inducers ≥ 10 days (Section 17.6)
- c. Proton pump inhibitors (eg, omeprazole, esomeprazole, lansoprazole, dexlansoprazole, and pantoprazole) ≥ 5 days

14. Female subjects of reproductive/childbearing potential with a male sexual partner must agree to use a highly effective form of contraception or avoid intercourse during and upon completion of the study and for at least 3 months after the last dose of study drug. For the purpose of this protocol, methods considered as highly effective birth control include:

- a. Combined (estrogen- and progestogen-containing) hormonal contraception associated with inhibition of ovulation (oral, intravaginal, or transdermal delivery). *
- b. Progestogen-only hormonal contraception associated with inhibition of ovulation (oral, injectable, or implantable delivery). *
- c. Intrauterine device (IUD).
- d. Intrauterine hormone-releasing system (IUS).
- e. Bilateral tubal occlusion.
- f. Vasectomized partner.
- g. Complete sexual abstinence.

Non-child-bearing potential is defined as pre-menopausal with documented tubal ligation or hysterectomy; OR postmenopausal with documented ≥ 12 months of spontaneous amenorrhea (in questionable cases, a blood sample with simultaneous follicle-stimulating hormone [FSH] > 40 mIU/mL and estradiol < 40 pg/mL [< 147 pmol/L] is confirmatory).

Females on hormone replacement therapy (HRT) and whose menopausal status is in doubt will be required to use one of the contraception methods outlined above for women of child-bearing potential if they wish to continue their HRT during the study. Otherwise, they must discontinue HRT to allow confirmation of post-

menopausal status prior to study enrollment. For most forms of HRT, at least 2 to 4 weeks must elapse between the cessation of therapy and the blood draw; this interval depends on the type and dosage of HRT. Following confirmation of their post-menopausal status, they can resume use of HRT during the study without use of a contraceptive method.

Female subjects must not retrieve ova or donate from the time of screening and throughout the study treatment period, and for ≥ 3 months after the final dose of study drug.

* Only oral agent are approved in Japan.

15. A male subject with a sexual partner who is a woman of child-bearing potential must be willing and able to use a highly effective contraceptive method for the entire study treatment period and for ≥ 3 months after the final dose of study drug.
 - a. Acceptable forms of contraception include condoms and highly effective contraception used by the usual female partner (see above for forms of highly effective contraception).
 - b. Male subjects must not freeze or donate sperm starting at screening and throughout the study period, and ≥ 3 months after the final dose of study drug.
16. Subjects must be fully informed about their illness and investigational nature of the protocol (including foreseeable risks and possible side effects) and sign and date an Institutional Review Board (IRB)/Institutional Ethics Committee (IEC)-approved Informed Consent Form (ICF) before performance of any study-specific procedures or tests.
17. Is willing and able to complete a daily study medication diary.

4.2. Exclusion Criteria

1. Has any evidence of small cell histology, or combined small cell and non-small cell histology, in original tumor biopsy or in screening biopsy performed since progression.
2. Has previously documented evidence of anaplastic lymphoma kinase (ALK) fusion, ROS proto-oncogene 1 (ROS1) fusion, BRAF V600E mutation, rearranged during transfection (RET) rearrangement, human epidermal growth factor receptor 2 (HER2) mutation, or MET exon 14 skipping mutation. No new testing for these genomic alterations is required for Screening.
3. Has received treatment with any of the following:
 - a. Any cytotoxic chemotherapy, investigational agent or other anticancer drug(s) from a previous cancer treatment regimen or clinical study (other than EGFR TKI), within 14 days of the first dose of study treatment
 - b. Immune checkpoint inhibitor therapy within 30 days of first dose of DS-1205c.
 - c. Major surgery (excluding placement of vascular access) within 4 weeks of the first dose of study treatment

- d. Radiotherapy treatment to more than 30% of the bone marrow or with a wide field of radiation within 4 weeks, or palliative radiation therapy within 2 weeks of the first dose of study drug treatment.
- 4. Has history of other active malignancy within 3 years prior to enrollment, except:
 - a. Adequately treated non-melanoma skin cancer OR
 - b. Superficial bladder tumors (Tumor stage “a” [Ta], Tumor stage “is” [Tis], Tumor stage “1” [T1]) OR
 - c. Curatively treated in situ disease OR
 - d. Low-risk non-metastatic prostate cancer (with Gleason score < 7 on antiandrogen therapy)
- 5. Clinically significant malabsorption syndrome or other gastrointestinal disease (eg, persistent diarrhea, or known sub-acute bowel obstruction \geq NCI-CTCAE v5.0 Grade 2, despite medical management) that would impact drug absorption.
- 6. Presence of retinal disease in the eye that is not due to neovascular age-related macular degeneration (nAMD; eg, significant diabetic retinopathy, glaucomatous retinal atrophy, retinal detachment).
- 7. Has spinal cord compression or clinically active brain metastases, defined as untreated and symptomatic, or requiring therapy with corticosteroids or anticonvulsants to control associated symptoms. Subjects with clinically inactive brain metastases may be included in the study. Subjects with treated brain metastases that are no longer symptomatic and who require no treatment with corticosteroids or anticonvulsants may be included in the study if they have recovered from the acute toxic effect of radiotherapy. A minimum of 2 weeks must have elapsed between the end of whole brain radiotherapy and study enrollment (1 week for stereotactic radiotherapy).
- 8. Has history of myocardial infarction within the past 6 months.
- 9. Has symptomatic congestive heart failure (New York Heart Association [NYHA] Classes II – IV), unstable angina, or cardiac arrhythmia requiring antiarrhythmic treatment.
- 10. Has LVEF < 45% by either ECHO or MUGA.
- 11. Has any clinically important abnormalities in rhythm, conduction or morphology of resting ECG, eg, complete left bundle branch block, third-degree heart block, second-degree heart block, or PR interval $>$ 250 ms.
- 12. Has a mean QTcF prolongation to $>$ 470 ms for females and $>$ 450 ms for males in three successive Screening measurements.
- 13. Unable or unwilling to discontinue concomitant drug that may influence gefitinib or DS-1205c metabolism.
- 14. Unable or unwilling to discontinue concomitant use of drugs that are known to prolong the QT interval. (See Section 17.6).

15. Has any factors that increase the risk of QTc prolongation or risk of arrhythmic events, such as congenital long QT syndrome, family history of long QT syndrome or unexplained sudden death under 40 years of age in first-degree relatives.
16. Has a history of (non-infectious) ILD/pneumonitis that required corticosteroid treatment, has current ILD/pneumonitis, or has suspected ILD/pneumonitis which cannot be ruled out by imaging at screening.
17. Has history of pancreatitis within the past 6 months.
18. Has any evidence of severe or uncontrolled systemic diseases including uncontrolled hypertension, active bleeding diatheses or active infection (including hepatitis B, hepatitis C, and human immunodeficiency virus [HIV]), psychiatric illness/social situations, substance abuse, or other factors which in the Investigator's opinion makes it undesirable for the subject to participate in the study or which would jeopardize compliance with the protocol. Screening for chronic conditions is not required.
19. Is a lactating mother (women who are willing to temporarily interrupt breastfeeding will also be excluded), or pregnant as confirmed by pregnancy tests performed within 7 days before enrollment.

